A routine colposcopy appointment will normally take on average 5 minutes, or if treatment is being performed may take 10-15minutes. The VR videos developed by Rescape last approximately 7 minutes each. There are 3 videos available that we can play back-to-back to ensure immersion in the VR intervention with no break. The videos have been specifically chosen to aid feelings of relaxation and include, walking through a forest while David Attenborough narrates and an under the sea diving experience through a shipwreck. Participants will still be able to hear the clinician throughout the colposcopy to allow them to stay informed of any procedural elements taking place. No other aspects of the participants care in colposcopy will be changed apart from the addition of the headset. All other forms of pain relief will be provided as required in normal colposcopy. This includes local anaesthetic to provide a cervical block and nitrous oxide for inhalation. The participant will be free at her own will to remove the headset at any stage, and this will be recorded as part of the assessment.

Once the colposcopy treatment is complete the participant will be assisted to remove the headset and informed the results of the colposcopy the routine manner. Participants who are part of the control arm of the study will have colposcopy performed as per standard practice with no VR headset application at the time.

Following the completion of the colposcopy, participants will then be asked by the research team to complete another short paper questionnaire (Appendix 5) to quantify their perceived pain and actual anxiety score during the procedure. This will be kept anonymised and blinded from the clinician who has carried out consultation.

Participants who were allocated to be in the control arm of the study will be offered the opportunity to trial a headset following completion of their enrolment in the study.

Following completion of patient interaction, the clinician who has carried out the procedure will be asked to fill out a paper questionnaire (Appendix 6) provided by the PI/CRN regarding the ease and timing of the procedure, and if any difficulties were encountered with the equipment or communication with the patient.

Staff Training

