All clinicians and clinic staff who will be involved in application of the headset to participants have had training from Rescape or PI on how to use to the system. The training video is available to all staff if they feel they need to renew their training. The training log has been recorded and will be added to the standard operating procedure file. (SOP).

Criteria for discontinuing or modifying allocated interventions

Participants are free to remove the VR headset at any point in the intervention. They will be informed of this prior to its application. Participants will be free withdraw consent and leave the trial at any point during the process. They do not have to give prior warning or any explanation. This will not change the clinical procedure being conducted. If participant becomes upset or display signs of anxiety during the procedure the distress protocol will be followed (Appendix 3)

There is a risk of cybersickness during the application of the headset. Patients will be informed of this during the consent process and informed to remove the headset should this occur. This is included in the distress protocol and the deviation log (Appendix 7).

Strategies to improve adherence to interventions

Potential participants will be shown photographs of the VR headset prior to enrolment in the trial via the PIL provided to ensure understanding of its involvement. If they are in the VR intervention arm, they will be given the opportunity to see the VR device prior to beginning the therapy. They will be given the opportunity to try the headset on prior to beginning the colposcopy consultation to ensure they are amenable to having it placed prior to the procedure.

Relevant concomitant care permitted or prohibited during the trial

Some patients attending colposcopy will only have an inspection performed of the cervix, other patients will have a biopsy or a LLETZ procedure performed. If a biopsy or LLETZ procedure is performed, the entire colposcopy experience will take longer and may be more painful than if only inspection is performed. If a patient needs a biopsy or LLETZ performed, this will not be known until the colposcopy inspection

has taken place, so it is not possible to stratify the study group arms prior to enrolment in the trial.

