Participants will complete a questionnaire (Appendix 6a) with STAI questions prior to randomisation to get a baseline anxiety level. This will be compared to the post procedural questionnaire (Appendix 6b) with the same questions to compare the actual anxiety levels during the procedure. Comparison will be made between the two arms.

Secondary Outcome

Pain reduction: Pain scores will be measured by a Numeric Rating Scale (NRS) from 0 through to 10. 0 represents “no pain” and 10 represents “worst pain imaginable”. This will be shown alongside a visual analogue scale (VAS) of pain on animated faces. This is a validated measure for pain, is easy to use, has high compliance rates and detects meaningful change. (29,30,31) Participants will be asked to state the “maximum pain felt, if only for one moment,” and also state the “average pain experienced,” throughout the procedure. Respondents will select the single number that best represents their pain intensity. Results from participants in the intervention arm will be compared to participants in the control arm.

Understanding the acceptability and effectiveness of VR in variations of patient demographics: Participants will be asked to state the following demographics – age, ethnicity, parity, menopausal status, previous attendances to colposcopy and previous treatments in colposcopy. Acceptability will be monitored by participants ongoing consent of using the VR headset. If a patient removes the headset before the colposcopy assessment is completed, this will be noted in the post procedural questionnaire and be noted that the patient did not find it acceptable. The demographics of this patient cohort will be reviewed to see how VR effects different patient demographics.

Feasibility and acceptance of intervention from clinicians’ perspective: Following completion of the colposcopy assessment, the clinician will be asked to complete a short survey of their experience using VR. (Appendix 6c) These will be questions on a Likert scale from “strongly disagree” to “strongly agree”. Clinicians will be asked did they find it easy to use the VR in their clinic, did they find it beneficial to the consultation, did they find it easy to communicate with the patient during the consultation.

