All adverse events will be reported. Depending on the nature of the adverse event the reporting procedures below will be followed. Any questions concerning adverse event reporting will be directed to the Primary Investigator (VB) in the first instance.

All SAEs will then be reported to [name] (CI) where in the opinion of the Chief Investigator, the event was:

- 'related', i.e., resulted from the administration of any of the research procedures; and
- 'unexpected', i.e., an event that is not listed in the protocol as an expected occurrence

Reports of related and unexpected SAEs should be submitted within 15 days of the Chief Investigator becoming aware of the event, using the NRES SAE form for non-IMP studies. The Chief Investigator must also notify the Sponsor of all SAEs.

Local investigators will report any SAEs as required by their Local Research Ethics Committee, Sponsor and/or Research & Development Office.

Plans for communicating important protocol amendments to relevant parties (e.g., trial participants, ethical committees)

Any modifications to the protocol which may impact on the conduct of the study, potential benefit of the patient or may affect patient safety, including changes of study objectives, study design, patient population, sample sizes, study procedures, or significant administrative aspects will require a formal amendment to the protocol. Such amendments will be agreed by the steering group and be approved by the ethics committee. All changes will be disseminated to the necessary clinicians via the research team and emails. Patients will be informed of any changes upon their arrival.

Dissemination plans

We would intend to publish our research protocol and then subsequent findings will be disseminated by publication in a high impact peer reviewed scientific journal of a gynaecological nature. E.g., British Journal of Obstetrics and Gynaecology (BJOG). Our objective is to complete a high quality randomised controlled trial that will be informative to various healthcare professionals – primarily gynaecologists and nurse colposcopists. We believe that this has the potential to change and develop future guidelines for other areas of medicine that frequently use outpatient procedures, such as colonoscopy, ENT, tissue viability nurses.

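### Cybersickness is captured only passively in the main text, so it is likely to be under-recorded and mixed with dislike of the headset; one symptom item for every patient would correct this

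*Combined protocol and SAP*

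**What the plan says.** All places are in the combined protocol and SAP.

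- **Criteria for discontinuing or modifying allocated interventions.** The harm is named: "There is a risk of cybersickness during the application of the headset". The response is left to the patient: "Patients will be informed of this during the consent process and informed to remove the headset should this occur". On where it is handled: "This is included in the distress protocol and the deviation log (Appendix 7". The only trigger that this section spells out for the distress protocol is a participant who is upset or shows anxiety. On leaving the trial, the section says of participants: "They do not have to give prior warning or any explanation".
- **Intervention description.** The post-procedure questionnaire is given "to quantify their perceived pain and actual anxiety score during the procedure". The clinician's form asks about ease, timing and "if any difficulties were encountered with the equipment or communication with the patient". Early removal of the headset is recorded. Local anaesthetic and nitrous oxide remain available in both arms.
- **Plans for assessment and collection of outcomes.** If the headset comes off early, "this will be noted in the post procedural questionnaire and be noted that the patient did not find it acceptable".
- **Provisions for post-trial care.** There is no routine follow-up for the study. Patients may ask questions and receive contact details.
- **Adverse-event reporting text.** "All adverse events will be reported", with no exclusion for cybersickness.
- **Outcomes and Statistical methods.** Neither section lists a safety outcome or a summary of symptoms or adverse events by arm.

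**The concern.** Each step in the described route needs something to happen first: the patient takes the headset off, is visibly distressed, or says something. A patient who feels queasy, stays calm and finishes the procedure with the headset on meets none of these conditions. The study has no routine follow-up, so the post-procedure questionnaire is the one planned contact at which everyone could be asked.

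Two results are affected. The first is the count of a device harm that the plan itself names. A low count obtained this way would probably be read as reassurance, since the background presents VR as avoiding the side effects of sedatives and the dissemination plan looks to other outpatient procedures. The second is acceptability, a secondary outcome measured by whether the headset stays on. A patient who removes it because she feels sick and one who removes it because she dislikes it are recorded the same way, although the two findings call for different responses.

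Controls matter too. Nausea or dizziness can come from the procedure or from nitrous oxide. Without the same question in both arms, there is no background rate to set beside the VR figure.

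**Working it through.** **1. Who would be counted under the route described**

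| Patient | What the main text describes |
|---|---|
| VR, feels sick, removes headset | Removal noted as non-acceptance; cause reaches the log only if staff learn of it |
| VR, feels sick, keeps headset on, tells staff | May be logged; no text says the entry is also an adverse event |
| VR, feels sick, keeps headset on, says nothing | No described route |
| VR, dislikes headset, removes it | Removal noted as non-acceptance, as in the first row |
| Control, nausea or dizziness | No question described |

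The third row produces the under-count. The first and fourth rows together blur acceptability.

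**2. Denominator**

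The plan gives no figure for cybersickness. The only related figure is the sample size. A two-sample t-test with d = 0.5, two-sided alpha 0.05 (sidedness is not stated, so this is assumed) and power 0.80 needs 63.77 per arm, hence 64 per arm and 128 in total, as the plan states. Its 10% addition is 128 × 1.10 = 140.8, rounded up to 141. At 1:1 allocation 141 / 2 = 70.5, so take 70 VR patients.

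**3. What asking everyone would give**

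- No events: exact two-sided 95% upper limit = 1 − 0.025^(1/70) = 5.1%.
- Seven events: 7/70 = 10%, exact 95% interval 4.1% to 19.5%.

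Precision is modest, but the statement is interpretable because the denominator is the number of patients asked.

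**4. What incomplete capture would do**

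Let p be the true rate and s the share of cases captured. Neither is in the documents; the values below are assumptions that show the range. Recorded rate = p × s; chance that no case is recorded among 70 = (1 − p × s)^70.

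| p | s | Expected recorded cases | Recorded rate | Chance of none recorded |
|---|---|---|---|---|
| 5% | 25% | 0.875 | 1.25% | 41% |
| 5% | 75% | 2.625 | 3.75% | 6.9% |
| 10% | 25% | 1.75 | 2.5% | 17% |
| 10% | 50% | 3.5 | 5.0% | 2.8% |
| 10% | 75% | 5.25 | 7.5% | 0.4% |
| 10% | 100% | 7 | 10% | 0.06% |
| 20% | 25% | 3.5 | 5.0% | 2.8% |
| 20% | 75% | 10.5 | 15% | 0.001% |

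The direction is fixed: missed cases lower the recorded rate. The size is not known, because s is not known.

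**The case against.** The strongest objection is that the forms themselves were not available: the post-procedure questionnaire (Appendix 5 in one section, 6b in another), the clinician form, the distress protocol (Appendix 3) and the deviation log (Appendix 7). Nor was the text directly before the adverse-event paragraph. The stated purpose of a form is not its item list. The sentence giving the purpose of the post-procedure questionnaire omits headset removal, yet another section says removal is noted there. A reader might infer that patients are not asked about symptoms. The documents do not support that; they support only that no such question is described. This stands, and it makes checking the appendices the first step.

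A reader might also infer that cybersickness is kept out of the adverse-event count, or that the two sections conflict. They do not. Being included in a log does not mean being reported there instead of as an adverse event, and the adverse-event rule has no exclusion. What is missing from the available text is the link between the two.

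Capture is also somewhat wider than headset removal. An assistant whose main role is to support the patient is always in the room, the clinician reports equipment difficulties, and patients leave with contact details. These routes should raise the share captured, but all of them still wait for someone to notice or volunteer something.

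Finally, safety is not a listed objective, the device is CE marked and described as in use in over 100 healthcare settings, and the illustrative rates are assumed. All of this is fair. It limits the importance of the point without changing the direction of the under-count.

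**Conclusion.** The point holds in a limited form. As described in the main text, capture of cybersickness is passive, no symptom question for every patient is described, headset removal is noted as non-acceptance without a reason, and no available text says that a log entry is also counted as an adverse event. Cybersickness is therefore likely to be under-recorded, and sickness is mixed with dislike in the acceptability outcome.

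The size of the under-count cannot be given. The 2.5% to 7.5% range rests on an assumed true rate of 10% and assumed capture of 25% to 75%, and is an illustration only. A reader might infer that the rate cannot be estimated at all. That goes too far: a log count over about 70 VR patients is a usable figure, but a probable underestimate.

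The primary anxiety comparison and the sample size are untouched. This is an inexpensive improvement, conditional on the appendices not already containing it.

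**What to change.** First check the appendices and the safety text before the adverse-event paragraph. If they already cover the points below, a cross-reference in the main text is enough. Otherwise:

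1. Add one fixed item to the post-procedure questionnaire in both arms: nausea, dizziness and headache, each none, mild, moderate or severe. Controls should answer before any optional try of the headset; symptoms arising during that try should be counted separately.
2. Record the reason for any early headset removal, where the patient is willing to give one, so that acceptability can be reported with symptoms separated from preference.
3. State that each cybersickness entry under the distress protocol or in the deviation log is also recorded as an adverse event.
4. In Statistical methods, plan symptom counts by arm with exact 95% confidence intervals.

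The cost is a short addition to existing paper forms and a few sentences of text. The sample size and the patient's freedom to remove the headset do not change. There is a downside: the recorded adverse-event rate will be higher. Because the trial is open-label and patients are warned of cybersickness at consent, prompted mild reports may also be somewhat more frequent in the VR arm. The report should say so when comparing arms.

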There are approximately 3200 new cases of cervical cancer diagnosed annually in the UK, with around 690 biological females dying from the disease. However, 99.8% of these cases are preventable. The numbers of cancer are consistently dropping, largely due to the advances in cervical screening and colposcopy, however screening attendance is at a 20 year low with one in four people with a cervix not participating. (1) More than 95% of cervical cancers are due to the human papilloma virus (HPV), particularly type 16 and 18. HPV is a common viral infection of the reproductive tract that most sexually active men and women will be infected by at some point of their lives. 90% of people will clear the infection themselves without any symptoms or treatment required, however HPV infection is a well-known risk factor for many types of cancer. If HPV does infect cervical epithelial cells, it changes the way cells interact with one another, causing the infected cells to multiply in an uncontrolled manner. (2) These can form the precancerous cells known as cervical intra-epithelial neoplasia (CIN). These changes, especially in young biological females, often revert to normal cells due to an appropriate immune response and the rapid proliferation of cells of the cervix. 60% of CIN-1 will regress to normal after 1 year. People with CIN-2 and CIN-3 are at higher risk for developing cervical cancer and so should receive treatment. Regular cervical smears enable early detection of cervical changes to CIN cascade and prompt referral to colposcopy for further investigation. (2,3)

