with clear margins. Various outcomes from the examination and procedure can mean many patients are invited to reattend for a further colposcopy in a few weeks or months – such as follow up following a biopsy, unclear margins, mismatch between clinical findings and histopathological findings or the specimen being upgraded to a cancer. (5) Hence, colposcopy is often not a one stop clinic for service users so anxiety may be increasingly heightened as time progresses.

Despite colposcopy having undeniable significance in biological female's healthcare, the entire process is associated with high levels of stress and anxiety for patients. Colposcopy is a unique circumstance due to the intimate nature of the examination and the association with cancer. It is associated with fear, stress and loss of control. Many studies show that patients experience a "very high" level of anxiety when attending for colposcopy. (6) In comparison to other medical procedures, biological female patients experience a higher level of anxiety when attending colposcopy than when they are attending for cardiac surgery. (6,7) Anxiety can negatively impact a person's cognitive abilities and decreases the ability to recall and act on advice, leading to patients being less likely to comply with any information given. (8) Higher pre-procedural anxiety is predictive of post operative pain reported by patients in gynecological settings. Thus, by addressing these feelings, clinicians can reduce pain perception, however reducing this during a procedure without pharmacological agents remains a difficult task. (9)

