Biological females attending colposcopy will be invited to take part a focus group to review our patient information leaflets, questionnaires and consent forms to ensure they are easily understandable by service users. We will use the focus groups to ensure the study runs in a way that the local patient population feel is beneficial to them.

The study has been presented at the regional colposcopy business meeting with a very strong consensus from clinical staff that this will be a worthwhile study to perform for patients attending colposcopy.

The research proposal was presented to the colposcopy staff at the monthly business meeting and to the gynaecological oncology team at an inaugurate annual research meeting. The proposal was met with enthusiasm from the team and everyone presented to was willing to take part. Feedback regarding logistics was given and incorporated into the proposal.

The study is aligned to current government aims of transforming the NHS for the future. We are living in an increasingly digitalised environment and further research and investment is needed in these advancing technologies. Use of VR is highly transferrable into other outpatient procedural settings which could improve patient experience globally. NICE guidance in 2018 has recommended that further studies be performed to investigate methods to reduce anxiety in biological females undergoing colposcopy in order to improve patient experience and reduce the number of patients lost to follow up.

Aim

The aim of this study is to assess the effectiveness of utilising Virtual Reality technology as a non-pharmacological intervention to alleviate anxiety, reduce pain perception, and enhance overall satisfaction for people with a cervix undergoing colposcopy procedures.

Nul hypothesis

The addition of virtual reality headsets to outpatient colposcopy as a form of digital digital has no effect on biological females measured anxiety or pain scores.

Objectives

Primary objective

- To determine if the addition of virtual reality headsets during outpatient colposcopy appointments has an impact on patients' anxiety perception compared to standard management.

Secondary objectives

- To determine if the addition of virtual reality headsets during outpatient colposcopy appointments has an impact on patients' pain perception compared to standard management

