- Understanding the acceptability and effectiveness regarding anxiety reduction of VR interventions within the procedural groups and how these might vary as a function of different patient demographics.
- Feasibility and acceptance of intervention from clinicians' perspective
- To investigate if the introduction of VR have an impact on patients' attendance to follow up appointments

Study Design

Trial design

The “Mind over Cervix” trial is designed as a single centre, prospective, non-blinded, randomised control trial with two parallel groups to determine the superiority of VR headsets in patients’ anxiety reduction and pain reduction during outpatient colposcopy compared to standard care.

Study setting

The study will be carried out in the colposcopy outpatient clinic in Queen Elizabeth Hospital (QE), Gateshead, Gateshead Health Trust.

QE is a large tertiary referral centre for gynaecology and colposcopy in the north-east of England. Over 1700 patients attend the department for colposcopy annually. (24) Colposcopy is provided by consultant gynaecologists, consultant gynaecologists and nurse colposcopists.

Withdrawal Criteria

Patients can withdraw from the study at any time and without giving a reason. Deciding to withdraw or not take part in the study will not have any effect on the standard of care they receive. In addition, any staff member may withdraw their consent at any time without giving a reason.

Recruitment

Queen Elizabeth Hospital in Gateshead is a large tertiary referral centre for Gynaecology and colposcopy in the northeast of England. Over 1700 patients attend the department for colposcopy annually. (24)

Following prospective ethical and trust approval via IRAS, all patients who attend for outpatient colposcopy will be informed of the study prior to their arrival to the department. They will be sent a patient invitation leaflet (Appendix 1) to their home through the post 2-4 weeks prior to their appointment to inform them of the study and the fact they may be approached. On arrival to the department, a poster will be displayed in the department to remind attendees of the study and the potential for their participation (Appendix 1a). They will be given information again via the PIL (Appendix 1b) which will be provided by the clerical staff when they attend reception to check in for their appointment.

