Provisions for post-trial care Patients that are enrolled into the study are covered by indemnity for negligent harm through the standard NHS Indemnity arrangements from Gateshead health trust. Following the procedure participants will be offered the opportunity to ask the team any questions. They will be provided with contact details for the study team if they have any concerns when they have left following the procedure.

Additional patient follow up will not routinely be performed as part of the study. Any follow up will be as per standard colposcopy practice.

Outcomes

[figure not shown]
Primary outcome

- To determine any change in anxiety experienced by people with a cervix attending for outpatient colposcopy as measured by STAI (state trait anxiety index) in both the intervention arm and the control arm. Pre procedure paper questionnaires will be conducted to establish a baseline anxiety measure for patients. The comparison will be performed from the post procedure paper questionnaires from both arms of the study.

Secondary outcomes

- To determine any change in pain experience by people with a cervix attending for outpatient colposcopy as measured by a numerical rating scale (NRS) in both the intervention arm and control arm via paper questionnaires.
- Understanding the acceptability and effectiveness of VR interventions within the procedural groups and how these might vary as a function of different patient demographics.
- Feasibility and acceptance of intervention from clinicians' perspective
- Does the introduction of VR have an impact on patients' attendance to follow up appointments?

Participant timeline

Sample size

The sample size calculation was run using the packages pwr and pwrss within R. For the calculation the significance level of 0.05 and power of 0.8 were used along with a Cohen's d of 0.5. Two different types of outcome variables will be used so the calculations used are based on ANCOVA (continuous) and the Mann-Whitney test (ordinal). Both results suggest a sample size of 64 participants in each group (128 in total). We have added on a 10% drop out rate which brings the total sample size to 141.

Assignment of interventions

Sequence generation and concealment mechanism

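### The protocol rules out stratification more broadly than its reason allows, and comparisons within procedural groups, if formed by the procedure performed, would not be protected by randomisation

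*Combined protocol and SAP*

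**What the plan says.** The section on relevant concomitant care notes that a visit with biopsy or LLETZ lasts longer and may hurt more than inspection alone. It says the need for either emerges only at inspection, and concludes "so it is not possible to stratify the study group arms prior to enrolment in the trial".

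Other sections bear on this:

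- The background says many patients are asked back, for reasons "such as follow up following a biopsy, unclear margins" among others. The eligibility criteria exclude women with more than one previous LLETZ, a previous conisation or uterine didelphis, so other returning patients can enter.
- The plans for outcome collection list "previous attendances to colposcopy and previous treatments in colposcopy" among the items participants report. Statistical methods includes previous attendance among the baseline values to be shown by arm.
- A secondary objective concerns "effectiveness regarding anxiety reduction of VR interventions within the procedural groups". The groups are not defined there or under Outcomes.
- Randomisation follows consent and the first questionnaire. In the VR arm the headset goes on before the examination starts, and the blinding section rules out masking once the arm is allocated.
- Statistical methods names ANCOVA and Mann-Whitney for anxiety. It names no covariates, procedure term, subgroup analysis or interaction test.

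**The concern.** There are two separate issues.

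First, the conclusion about stratification outruns its premise. An unknown procedure cannot be a stratum. A woman's colposcopy history is a different variable, already fixed when she picks an envelope. As worded, the statement could lead the trial team to leave a usable baseline factor out of both design and analysis, with some cost in chance imbalance and precision.

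Second, the procedural-groups objective needs groups, and the natural reading of the concomitant-care section is inspection, biopsy or LLETZ as performed. Membership is then settled after allocation by a clinician who can see the headset. The protocol's own rationale expects VR to reduce abandoned procedures. If it does, the VR women in a treated-in-clinic group could include some whose control counterparts did not complete treatment. A difference seen inside that group would mix the effect of VR with a difference in who is there. At stake is a secondary result that could be reported as randomised evidence when it is not.

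**Working it through.** **The plan's own figure.** Inputs from Sample size: "significance level of 0.05 and power of 0.8 were used along with a Cohen's d of 0.5". Sidedness is not stated. The null hypothesis that VR "has no effect on biological females measured anxiety or pain scores" suggests a two-sided test. A two-sample t-test then needs 63.77, so 64 per arm, which agrees with "Both results suggest a sample size of 64 participants in each group (128 in total"). Adding 10% gives 128 × 1.10 = 140.8, so 141. The planned size is reproduced and has no allowance for subgroups.

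**What is known, and when.**

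| Item | Settled | Usable as stratum or covariate? |
|---|---|---|
| Previous attendance, previous treatment | Before consent | Yes |
| Arm | After the first questionnaire | – |
| Inspection, biopsy or LLETZ | During the examination, after allocation | No |
| Procedure completed or abandoned | During the examination, after allocation | No |

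The protocol's reason applies to the third row. Its conclusion, as worded, also covers the first.

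**Chance imbalance in a baseline factor.** For a yes/no factor held by a share p of patients, with 64 per arm and no stratification, the SD of the between-arm difference is √[p(1 − p) × 2/64]. The documents give no value of p, so the shares are assumptions.

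| Assumed share p | SD of difference | Chance of a gap above 10 points |
|---|---|---|
| 20% | √(0.16 × 0.03125) = 7.1 points | 16% |
| 30% | √(0.21 × 0.03125) = 8.1 points | 22% |
| 50% | √(0.25 × 0.03125) = 8.8 points | 26% |

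To translate this to the outcome, assume the factor shifts STAI by 0.5 to 1.0 SD. A 10-point gap then moves the contrast by 0.10 × 0.5 = 0.05 to 0.10 × 1.0 = 0.10 SD, before any baseline adjustment and against a planned effect of 0.5 SD.

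**Power inside a procedural group.** If a share s of patients has the procedure, the group holds 64s per arm. Power is for d = 0.5, two-sided 5%. The interaction column is for a difference in VR effect of 0.5 SD between that group and the rest, with standard error √[2/(64s) + 2/(64(1 − s))]. The shares are again assumed.

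| Assumed share s | Per arm in group | Power within group | Power for interaction | Evaluable total for 64 per arm in group (128/s) |
|---|---|---|---|---|
| 20% | about 13 | 23% | 21% | 640 |
| 30% | about 19 | 33% | 25% | 427 |
| 50% | 32 | 50% | 29% | 256 |

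So even with no selection at all, within-group results from this trial would be imprecise.

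**The case against.** The strongest reply is that the concomitant-care paragraph is only about procedure type. Read that way, it says the arms cannot be stratified by procedure, which is consistent with the rest of the document, and the plan does treat previous attendance as available. This stands in part: the fault is over-broad wording, and the baseline factor is still not given any role in the analysis.

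A reader might infer that the statement is simply wrong for returning patients, because their procedure is known at consent. The background does say "People with CIN-2 and CIN-3 are at higher risk for developing cervical cancer and so should receive treatment", but that is general and does not say when treatment is decided. Elsewhere the protocol makes biopsy or LLETZ depend on what the examination shows. The documents establish that history and the reason for returning can be known beforehand, not that the day's procedure is.

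A reader might also infer that stratifying would rescue the procedural-groups objective. It would not: the procedure performed would still arise after randomisation.

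On bias, the other side notes that abandonment is not the same as the indication to biopsy or treat, and that the protocol says care is otherwise unchanged. Both are fair. No passage shows that seeing the headset alters the colposcopist's decision. But unchanged care does not settle whether a procedure is completed, so the selection route through completion remains open.

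Finally, attendance history is not procedure type. A woman newly referred from later screening may have attended before. That limits what the covariate can do.

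**Conclusion.** The point holds in a limited form. The statement on stratification is broader than its reason. Previous attendance and treatment are pre-randomisation factors that the analysis could use. Within-procedure contrasts, on the natural reading of the undefined groups, are not protected by randomisation and have no stated analysis.

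It should not be read as saying that the main result is compromised. The comparison of the randomised arms is valid without stratification; what is lost is some balance and precision. Nor do the documents demonstrate biased within-group results.

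The size is moderate. With 64 per arm, chance imbalance has an SD of 7.1 to 8.8 percentage points, and within-group power is 23% to 50%, both over assumed shares of 20% to 50%. The STAI shift of 0.5 to 1.0 SD is also an assumption. The change is worth making because it is cheap and prevents a non-randomised comparison from being presented as a randomised one.

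**What to change.** 1. Reword the concomitant-care statement to say that only stratification by procedure is not possible.
2. Pre-specify previous attendance or treatment (yes/no), alongside baseline STAI, as a covariate in the anxiety ANCOVA, and include it in the pain model. A plain Mann-Whitney test takes no covariate, so pain needs a regression model or a stratified rank test. Confirm that the item is answered before the envelope is chosen; the questionnaires are not in the text available.
3. Define the procedural groups. Record the procedure performed and whether it was completed, and tabulate both by arm.
4. Report within-procedure results as exploratory, non-randomised estimates with confidence intervals. Base any confirmatory subgroup statement only on the pre-randomisation factor.

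The cost is protocol wording, one model term and a table. The sample size stays at 128 evaluable and 141 in total. Using a covariate also avoids the separate envelope stacks that stratification would need and that choosing one of two envelopes does not provide. The downside is that previous attendance is a weak proxy for procedure, so the gain in precision may be small.
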